Messages are personalized based on first names, personal reasons for quitting, and amount of money to be saved based on individual smoking habits and price paid per pack. Texts are also tailored based on responses to text questions (e.g., whether or not they have smoked or practiced mindfulness). Texts include messages timed around major holidays and personalized messages on participants' birthdays. Picture messages are included based on our initial qualitative work. Our previously developed program sent 2-3 messages per day during Week 1, 3-4/day during Week 2, 4-5/day during Week 3, 5-7/day during Week 4, 6-7/day during Week 5, 4/day during Week 6, and 3-4/day during Week 7 (See Appendix for example text messages and [name] et al. 2019²⁰ for details on the pilot study). Based on feedback from our previous message testing, message timing and frequency is more flexible and personalized for the current project. This study offers participants the option to be included in the frequency of their choice (e.g.: very low, low, medium, high, very high) as well as a 12-hour time slot of their choice (e.g.: 7am-7pm or 10am-10pm). Text messages will periodically ask participants about their preferred text message frequency and timing so that participants can change their message schedule as needed.

Financial Compensation and Retention Procedures. Participants receive financial compensation for the time and inconvenience associated with participation, as well as parking validation/MARTA vouchers to defray the cost of travel. Participants will be compensated up to \$30 for assessments during weeks 1, 3, and 5, for a total of \$90. (Specifically, for each of the week 1, 3 and 5 assessments, which take place online, participants will be compensated \$25 for doing the survey and a \$5 bonus if they do it within 24 hours). Participants will be compensated \$40 for the assessment completed at week 8 (this is an in-person visit). Participants will be compensated \$60 for the first post-treatment follow-up assessment at week 12 and \$70 for the second post-treatment follow-up assessment at week 24 (both follow-up visits are in-person visits). Participants will also be compensated \$5 per survey for the every other day surveys, for a total of \$120 for all 6 weeks. Maximum compensation per person for completing all aspects of the study is \$380.

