- Participants will complete *Program Evaluations* to provide for their feedback about and suggestions for improving the intervention (both MBAT and iQuit Mindfully text messages). Usual care participants will answer 1 program evaluation question: "On the scale below, please circle the number that best represents whether you would recommend this quit smoking program (or something similar) for others who are interested in quitting smoking." (rated on 1-10 scale).

The maximum time between telephone screening and enrollment will be 1 month. The maximum time between baseline assessment and start of treatment will be 1 month. However, we will employ a variety of strategies to ensure that these timeframes are as short as possible. For example, in order to reduce the time between telephone screening and baseline we will offer a variety of days and times for baseline assessment. We will also time our recruitment efforts around planned baseline assessments to maximize potential participants' interest (in order to prevent longer wait time to accrue a sufficient number of participants to start a group).

Electronic Diary Assessments. *Electronic Diary Assessments* (also referred to as short-surveys) will be administered in the evening on every other day from Week 2 to Week 8, thus capturing key processes surrounding quitting smoking. Diary assessments will assess smoking behavior ("How many cigarettes did you smoke today?") and each of the hypothesized mechanisms (mindfulness, emotions, craving and withdrawal, self-efficacy, and social support). Participants will also indicate their mindfulness practice that day (See Appendix). Participants will receive an email and/or text with the REDCap link to the electronic diary assessment survey. Both participant-initiated options allow respondents to complete assessments at a time that is convenient to them between that evening and the next morning (by 9am).

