The relationship between treatment condition and each dichotomous study outcome (smoking cessation, lapse recovery) will be assessed with a generalized linear mixed model (GzLMM) with a Binomial distribution and logit link function. This is an appropriate statistical model with repeated measures data collected over time. ⁴⁴ A 2-level multilevel GzLMM will be specified, with time nested within subject. This approach will properly account for the multilevel data structure. Fixed effects considered in each model will include demographics, baseline nicotine dependence, treatment condition and time as main effects, and a treatment condition by time interaction. Testing of covariance structure will be conducted, and information criteria will be used to assess model fit and selection. Linear contrasts will be built into the analysis to estimate specific comparative effects of all treatment conditions. To test treatment effects on primary smoking cessation outcomes, repeated measures outcomes will be biochemically-confirmed 7-day point prevalence abstinence at weeks 8, 12, and 24. To test treatment effects on lapse recovery, this analysis will also be conducted among participants classified as smoking at the last treatment session. ¹² In addition, gender and race/ethnicity will be assessed as potential moderators of treatment effects.

The moderating effect of poverty status will be examined with the addition of a poverty status by treatment condition interaction into the models described in 1a). This will be tested using both dichotomous (i.e., below vs. at or above federal poverty threshold) and continuous poverty status variables (i.e., depth of poverty as indicated by income-to-poverty ratio and income deficit/surplus) according to U.S. Census guidelines.^{45,46}

Aim II. Investigate the mechanisms through which mindfulness training impacts smoking cessation.

Hypotheses regarding mechanisms will be tested with both traditional questionnaire data (collected from baseline through 24 weeks after the start of treatment) and electronic diary data (collected for 6 continuous weeks during treatment), separately. Mediation testing will be conducted regardless of statistical significance of intervention effects because of statistical, conceptual, and practical reasons for testing mediation in such cases.⁴⁷ Volatility will be calculated using the mean square successive

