difference (MSSD; 48 average of the squared difference between successive observations at times i + 1 and i) to capture both within-person variability and temporal instability. Mediation will be examined with multilevel mediation analyses for binary outcomes in the developed GzLMM. Bootstrapping with 5000 replications will be used to estimate standard errors and p-values for indirect effects. In addition to mediators of associations between treatment and abstinence outcomes, we will test more fine-grained day-to-day associations using electronic daily diaries.

We will test moderated mediation using a model proposed by Preacher, Rucker, and Hayes⁴⁹ that fits the hypothesized model (Figure 3), as the independent variable (mindfulness training) also functions as a moderator. Kline⁵⁰ termed this "second-stage moderation," as the second path of the indirect effect of the predictor on the dependent variable depends on the moderator. Conditional mediation and moderation effects will be tested using bootstrapping methods.⁴⁹ GzLMM provides an ideal method for assessing the proximal relation between negative affect/craving at a given assessment and smoking at the next assessment (using both questionnaire and daily diary data). For example, using daily diary assessments, we will examine whether the association between negative affect on a given day and next-day smoking is weaker among MBAT vs. UC participants.

Missing Data. Although there is no complete, comprehensive method for handling missing data for generalized linear mixed models, there are several different approaches that we can draw upon to address this issue.⁴⁴ We will use multiple imputation of missing data whereby missing observations for individuals are estimated based on baseline responses and other study covariates, and perform additional sensitivity analyses regarding various missing data assumptions for smoking outcomes.⁵¹

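### The diary's smoking item asks about 'today' but can be answered until 9am the next morning, so the reference day is ambiguous for responses after midnight

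*Combined protocol and SAP*

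**What the plan says.** Section 6.2 (Electronic Diary Assessments) says that the diaries "will be administered in the evening on every other day from Week 2 to Week 8". The smoking item is given as "How many cigarettes did you smoke today". Participants may "complete assessments at a time that is convenient to them between that evening and the next morning (by 9am". The intended reference day can be inferred from the mindfulness practice item: "Participants will also indicate their mindfulness practice that day (See Appendix". The full diary is in that Appendix, which is not part of the published text. The wording of the affect, craving and other mechanism items is therefore not visible.

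Section 9 (Aim II) uses the diary at day level. It describes the mixed model as a way of "assessing the proximal relation between negative affect/craving at a given assessment and smoking at the next assessment", and gives this example: "we will examine whether the association between negative affect on a given day and next-day smoking is weaker among MBAT vs. UC participants". Section 9 has no rule for assigning a response after midnight to a day and no sensitivity analysis for such responses.

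The primary analysis does not use the diary. In Section 9 its "repeated measures outcomes will be biochemically-confirmed 7-day point prevalence abstinence at weeks 8, 12, and 24".

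**The concern.** The item's recall period conflicts with its own response window. The protocol expressly allows an answer at 8am the next day, so such a response is compliant. A participant who takes 'today' at its word then counts cigarettes since waking on the following day. Another participant answering at the same hour may think back to the previous day. Both records look alike in the data.

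Hypothesis 2b asks whether mindfulness training weakens the link from negative affect and craving to later smoking. That analysis depends on knowing which day each smoking count belongs to. A mixture of full-day counts and part-day counts from the next day adds error to the outcome and alters the lag. The fault is separate from the every-other-day spacing of the diaries and would remain if they were daily.

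**Working it through.** The plan gives no completion times, misdating rate or related figure, so there is nothing to reproduce. The check starts with the text; the sizes that follow are illustrations.

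**Step 1: which day is reported.** Call the diary day D. The survey is sent on the evening of D, the window closes at 9am on D+1, and the next survey goes out on the evening of D+2.

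| Time of answer | Reading of 'today' | Day reported |
|---|---|---|
| Before midnight | Only one reading | D, as intended |
| Midnight to 9am | The day the survey was sent | D, as intended |
| Midnight to 9am | The calendar day of answering | D+1, at most its first 9 hours |

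Only the third row is in error, but it cannot be separated from the second. A completion time shows when the participant answered, not which day was meant.

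**Step 2: effect on the lag.** Suppose affect is reported for D and smoking is taken from the next diary. The intended gap is (D+2) − D = 2 days. If the next smoking item is answered in the morning and read literally, the gap is (D+3) − D = 3 days, and the count covers only the early hours of that day. Whether affect and craving shift too depends on item wording in the Appendix.

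**Step 3: inputs for size.**
- Paid diaries per person: $120 / $5 = 24 (Section 5, Financial Compensation and Retention Procedures).
- m, share of diaries answered after midnight: not given; assumed 10% to 50%.
- q, share of those read literally: not given; assumed 0% to 100%.
- s, chance that a literal reader has not yet smoked when answering, given that D was a smoking day: not given; assumed 10% to 50%.
- True mean of 8 cigarettes a day, with about 1 reported by a literal morning reader: both assumed.

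**Step 4: share of diaries misdated = m × q.**
- q = 0, any m: 0, so 0 of 24 diaries.
- m = 0.10, q = 0.5: 0.05, and 0.05 × 24 = 1.2 diaries.
- m = 0.40, q = 0.5: 0.20, and 0.20 × 24 = 4.8 diaries.
- m = 0.50, q = 1: 0.50, and 0.50 × 24 = 12 diaries.

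**Step 5: recorded mean = (1 − mq) × 8 + mq × 1.**
- q = 0: 8.0, no shortfall.
- m = 0.20, q = 0.5: 0.9 × 8 + 0.1 × 1 = 7.3, a shortfall of 0.7.
- m = 0.40, q = 0.5: 0.8 × 8 + 0.2 × 1 = 6.6, a shortfall of 1.4.
- m = 0.50, q = 1: 0.5 × 8 + 0.5 × 1 = 4.5, a shortfall of 3.5.

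**Step 6: share of smoking days recorded as zero = m × q × s.**
- q = 0: 0%.
- m = 0.3, q = 1, s = 0.1: 3%.
- m = 0.3, q = 0.5, s = 0.5: 7.5%.
- m = 0.5, q = 1, s = 0.5: 25%.

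Every range includes zero, and the documents do not say where within it the trial would fall.

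**The case against.** The strongest reply is that participants will understand what is meant. The survey arrives in the evening and the practice item points to the diary day, so most may answer for that day whenever they open the link. The Appendix diary may carry a date or an instruction that settles the matter. This stands as a limit on what can be claimed: the text shows an ambiguity, not an error rate. It does not remove the ambiguity, because the one smoking item the protocol quotes carries no date.

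A second reply is that completion times would let the analyst set aside after-midnight entries without any rewording. That is partly right. Exclusion also discards correct answers, however, and people who answer late may differ from those who do not.

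Two stronger readings are tempting, and the documents do not support either.

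- A reader might infer that morning responders do report the wrong day and that smoking days are entered as smoke-free. Nothing shows how participants read the item or how many answer in the morning. Section 5 (Nicotine Replacement Therapy) provides for participants who smoke within half an hour of waking, so a literal morning answer may be a low count rather than zero.
- A reader might infer a spurious treatment effect. If 40% of usual care diaries and 20% of text-arm diaries were answered in the morning, Step 5 would give 6.6 against 7.3, a false difference of 0.7 cigarettes a day. Those shares have no source. Section 6.2 describes one delivery route for the diary link, and the reminders in Section 5 are not restricted by arm. In this example usual care would record less smoking, so the artefact would work against the text arm. A difference by arm is possible but not shown.

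The reach is also limited. Section 9 tests mechanisms with questionnaire and diary data separately, so the diary is not the only evidence on hypothesis 2b. The mediation outcome in hypothesis 2a is abstinence.

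**Conclusion.** The concern holds as an ambiguity in measurement. In the published text, the smoking item's reference day is undefined for answers given between midnight and 9am, and no rule resolves it. Confidence in that is high, subject to what the Appendix diary says. Confidence in any particular size is low: the share misdated is m × q, which runs from 0% to 50% on the assumed ranges and is zero if all participants answer for the diary day.

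What is at risk is the diary part of Aim II, chiefly the lagged affect and craving to smoking associations of hypothesis 2b. Negative affect volatility, which is built from successive differences, would be touched only if the affect items share the same undated wording, and this cannot be seen. The primary abstinence outcome is unaffected. The point is a modest one on a secondary aim, but worth acting on because the remedy is cheap and the intended day cannot be fully recovered afterwards.

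**What to change.** First check the Appendix diary. If its items already name a date or instruct morning responders, confirming this in Section 6.2 settles the wording.

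Otherwise:
1. Replace 'today' in the diary items with the target date, piped by REDCap from the send date, for example: How many cigarettes did you smoke on Tuesday, June 15?
2. Index each diary by its target day, not by its submission time, and state this in Section 9.
3. Keep the 9am cut-off, retain the completion timestamp, and pre-specify the diary analyses with and without after-midnight entries. Section 10 mentions REDCap audit trails but not this use of completion times, so the team should confirm that they are stored.
4. Flag diaries collected under the undated wording, so that entries before and after the change can be told apart.

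The cost is a minor survey amendment with IRB review, and the flag in the data set. There are no added visits and no added participant burden. For diaries already collected, the sensitivity analysis is the only remedy, and it is a partial one.

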7. SAFETY ASSESSMENTS

Reporting of Adverse Events and Serious Adverse Events

An **adverse event (AE)** is defined as any unfavorable and unintended diagnosis, symptom, sign, syndrome or disease which either occurs during the study, having been absent at baseline, or if present at baseline, appears to worsen. Adverse events are to be recorded regardless of their relationship to the study intervention.

A **serious adverse event (SAE)** is defined as any untoward medical occurrence that results in death, is life threatening, requires inpatient hospitalization or prolongation of existing hospitalization, results in persistent or significant disability/incapacity, or is a congenital anomaly.

[name] will conduct daily oversight of participant safety, and will meet regularly with staff to review progress and discuss any problems or concerns. Adverse events that are not deemed "serious adverse events" will be included in the final report to the investigators, IRB, and NCI.

SAEs that are unanticipated, serious, and possibly related to the study intervention will be reported to the IRB and NCI in accordance with requirements. Georgia State University defines an unanticipated event as an event that was (1) unforeseen; (2) more likely than not related to the research; and (3) either caused harm to participants or others, or placed them at increased risk of harm. Unanticipated events include any harm or injury (physical, psychological, social or economic) or other unexpected events occurring during the course of participation in a research study. As required by the GSU IRB, [name] will report a summary of each unanticipated event to the IRB using the IRB Unanticipated Event form within 7 business days.

Unexpected fatal or life-threatening SAEs related to the intervention will also be reported to the NCI Program Officer and investigators within 7 days. Other serious and unexpected AEs related to the intervention will be reported to the NCI Program Official within 15 days. Anticipated or unrelated SAEs will be handled in a less urgent manner but will be reported to the IRB and NCI.

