5. STUDY INTERVENTIONS

Nicotine Replacement Therapy (*all conditions*). Nicotine patch therapy for participants who smoke >10 cigarettes/day will consist of 4 weeks of 21 mg patches, 2 weeks of 14 mg patches, and 2 weeks of 7 mg patches. Patch therapy for participants who smoke 5-10 cigarettes/day will consist of 4 weeks of 14 mg patches and 4 weeks of 7 mg patches. Nicotine lozenge therapy for participants who smoke their first cigarette within 30 minutes of waking will consist of 8 weeks of 4mg mini lozenges (6-9 4mg mini lozenges per day). Nicotine lozenge therapy for participants who smoke their first cigarette over 30 minutes of waking will consist of 8 weeks of 2mg mini lozenges (6-9 2mg mini lozenges per day).

Participants will receive 4 weeks of nicotine patches and lozenges at baseline, and they will be mailed the additional 4 weeks of nicotine replacement therapy when needed. Research staff will confirm participants' mailing addresses with them over the phone and notify them of the mail date for the nicotine patches and lozenges. Patches will be mailed to participants in padded envelopes via certified mail with 2-day delivery. The package will include the nicotine patch instructions and a cover page indicating: "When you receive this, please call [Research staff telephone number] so that we can go over it with you." Participants will also be told to call research staff with any side effects or questions.

In the unlikely case that a woman becomes pregnant during the study (since we are now excluding those who plan to become pregnant), she will still have access to all of the behavioral treatment depending on her treatment condition (MBAT groups, text messages, self-help materials), but she will be referred to her healthcare provider to inquire about and potentially obtain nicotine replacement therapy

Self-Help Materials *(all conditions)*. All participants will be given evidence-based self-help materials for smoking cessation (based on the *Treating Tobacco Use and Dependence Clinical Practice Guideline*). ¹⁸ Materials include the "Clearing the Air" booklet developed by the NCI and a referral to the Tobacco Cessation Quitline ([name]). Paper materials will be given at baseline and then reviewed in detail at treatment session 1 (with additional copies provided as needed).

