6. STUDY PROCEDURES

6.1 Schedule of Treatment Procedures and Evaluations

			Weeks									
	Phone/ Online Screen	Base- line	1 Start of Tx	2	3	4	5	6	7	8 End of Tx	12 (3 Month Follow- Up)	24 (6 Month Follow- Up)
Telephone/Online Screening	Х											
Compensation			\$30		\$30		\$30			\$40	\$60	\$70
Electronic Diary Assessments		Every	other day	surveys 1	from week	2 to wee	k 8; \$5 pe	r survey 1	or up to \$1	20 total		
TREATMENT PROCEDURES												
Virtual MBAT groups (MBAT & MBAT + iQuit Mindfully conditions)			Tx 1	Tx 2	Tx 3	Tx 4	Tx 5	Tx 6	Tx 7	Tx 8		
iQuit Mindfully text messages (iQuit Mindfully & MBAT + iQuit Mindfully conditions)		Text messages based upon participants' choice in frequency and timing of messages										
Self-Help Materials (all conditions)		Χ	X									
Nicotine Replacement Therapy Dispensation (all)			Participants receive 4 weeks of patches and lozenges in person at baseline, and then the remaining 4 weeks of patches are mailed.									
IN-PERSON ELIGIBILITY												
Carbon Monoxide		Х								Х	Х	Х
Cotinine (Saliva Sample)												Х
Screening for Depression and Substance Dependence		Х										
SMOKING												
Information for Setting Up Text Messages		Х										
Tobacco History	Х											
Smoking Status, use of other tobacco products, electronic vapor products, NRT, pharmacotherapy		Х	Х		Х		Х			Х	X	Х

	Phone/ Online Screen	Base- line	1 Start of Tx	2	3	4	5	6	7	8 End of Tx	12 (3 Month Follow- Up)	24 (6 Month Follow- Up)
Additional Resources Used for Smoking Cessation										Х	X	X
Wisconsin Inventory of Smoking Dependence Motives (WISDM)		Х								Х	Х	Х
Wisconsin Smoking Withdrawal Scale (WSWS)			Х		Х		Х			Х	Х	Х
Self-Efficacy Scale		Х	Х		Х		Χ			Х	Х	Х
MINDFULNESS												
Mindfulness Attention Awareness Scale (MAAS)		Х								Х	Х	Х
Five Facet Mindfulness Questionnaire (FFMQ short form)		Х								Х	Х	Х
Mindfulness Practice Frequency					Х		Х			Х	Х	Х
Self-Compassion Scale (short form)		Х								Х	Х	Х
STRESS/ NEGATIVE AFFECT												
Perceived Stress Scale		Х								Х	Х	Х
Positive and Negative Affect Scale		Х	Х		Х		Х			Х	Х	Х
Experiences with Discrimination		Х										
SOCIAL SUPPORT												
Multidimensional Scale of Perceived Social Support			Х							Х	Х	Х
Group Climate Questionnaire (MBAT & MBAT + iQuit Mindfully)										Х		
PROGRAM EVALUATION												
Text Message Feedback					Х		Х				Х	Х
Perceived Benefits										Х	Χ	Х
Program Evaluation Questionnaire										X		

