Individuals who would like to participate and express informed consent will then be asked to complete questionnaires (see Appendix). Questionnaires will be administered through REDCap, to be taken either in-person at GSU (baseline and weeks 8, 12, and 24) or off site (REDCap links to be emailed/texted when participants do not come to GSU in person). See Table 6.1 for schedule of questionnaire assessments. Descriptions of the assessments are provided below:

- The *Telephone Screening* assesses eligibility criteria and demographic characteristics, including age, race, ethnicity, education, employment, and income.
- The *Patient Health Questionnaire-2* PHQ-2; ^{22,23} is a 2-item questionnaire designed to screen for symptoms of depression. Participants are asked, "Over the last 2 weeks, how often have you been bothered by the following problems?": "feeling down, depressed or hopeless" and "little interest or pleasure in doing things." These items which correspond to the two core diagnostic criteria for Major Depressive Disorder; ²⁶ are rated on a 0-3 scale (0 = not at all, 3 = nearly every day). Individuals with scores of 3 or above which has been identified as the cut-off for obtaining optimal sensitivity and specificity for identifying depressive disorders; ^{22,23} will not be eligible but will be provided with appropriate mental health referrals.
- The Severity of Dependence Scale (SDS) is a 5-item questionnaire that measures the extent of psychological dependence on illicit drugs in the past 12 months.²⁴ The scale has been validated for several illicit drugs including cannabis, cocaine, amphetamines, benzodiazepines, and heroin. Each of the five items is scored on a 4-point scale ranging from 0 (Never/Almost Never) to 3 (Always/Nearly Always) and summed for a total score. Individuals with scores of 4 or higher^{27,28} will not be eligible but will be provided with appropriate mental health referrals.
- The Information for Setting Up Text Messages questions assess participants' amount of money spent on cigarettes, personal reasons for quitting, preferences about timing and frequency of text messages, and quit date. This information is incorporated into iQuit Mindfully to personalize the content, frequency and timing of text messages.

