8. INTERVENTION DISCONTINUATION

This study will be stopped prior to its completion if: (1) the intervention is associated with adverse effects that call into question the safety of the intervention; (2) any new information becomes available during the trial that necessitates stopping the trial; or (3) other situations occur that might warrant stopping the trial.

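### All adverse events must be recorded, but no visible scheduled assessment asks about them, and opportunities to mention one to staff differ by arm

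*Combined protocol and SAP*

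**What the plan says.** Section 7 sets a broad duty: "Adverse events are to be recorded regardless of their relationship to the study intervention". It defines an event by change, "having been absent at baseline, or if present at baseline, appears to worsen", and gives reporting deadlines. It does not say who asks participants, when, or on what form. On oversight it says that a named role "will conduct daily oversight of participant safety, and will meet regularly with staff to review progress and discuss any problems or concerns".

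For the schedule, Section 6.2 points to the table: "See Table 6.1 for schedule of questionnaire assessments". Table 6.1 has blocks for eligibility, smoking, mindfulness, stress and negative affect, social support, and program evaluation. The row closest to safety is "Smoking Status, use of other tobacco products, electronic vapor products, NRT, pharmacotherapy", which records use of products and not their side effects. The diary starts from smoking ("Diary assessments will assess smoking behavior") and adds the hypothesised mechanisms and mindfulness practice.

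The one stated route for side effects is in Section 5, under nicotine replacement for all conditions: "Participants will also be told to call research staff with any side effects or questions".

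Section 8 makes it the first ground for stopping the study that "the intervention is associated with adverse effects that call into question the safety of the intervention". Section 9 describes no analysis of adverse events.

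**The concern.** A duty to record everything, without a scheduled question, amounts to spontaneous reporting. What is recorded then depends on how often a participant has a live opportunity to mention a problem, and here the randomised treatment itself changes that. The two MBAT arms meet instructors and staff weekly. Usual-care and text-only participants fill in surveys, and their first scheduled in-person visit after baseline is at week 8. The texts are sent by an automated system, so the text-only arm gains no scheduled live contact from them.

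Two things are at stake. First, at the same true risk the MBAT arms would tend to show more recorded events, which could be read as harm from MBAT in the final report or in a judgement under the first stopping criterion. Second, all four arms receive nicotine patches and lozenges, and 195 of the 485 planned participants (145 text-only plus 50 usual care) are in the low-contact arms, where events might never reach staff.

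**Working it through.** **Is there a scheduled enquiry?** I read Table 6.1 row by row, then each instrument description in Section 6.2. None is described as asking about adverse events, side effects or hospital admissions. The oversight sentence in Section 7 concerns problems that have already surfaced. The definition also needs a baseline state to compare with, and no baseline symptom enquiry for that purpose is listed. The count of visible scheduled enquiries is therefore 0 in every arm.

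**Scheduled live staff contacts, weeks 1 to 8.**
- MBAT arms: 8 weekly sessions (Section 5) + the week 8 visit = 9.
- Usual care and text-only: the week 8 visit = 1.

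This leaves out the group Zoom orientation, which only the MBAT arms have and which comes before session 1. Staff also admit each MBAT participant individually to a breakout room at connection (Section 6.2), so these contacts include one-to-one moments.

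**Contacts that reach all arms.**
- Section 5 implies about two calls for the mailed nicotine replacement: staff confirm the address by phone, and the package asks the participant to call on receipt.
- The version 3 entry of the revision history allows the surveys at weeks 1, 3 and 5 to be done by phone. If everyone chose that, it adds 3.
- Section 5 also lists check-ins and reminder calls, with no number and no content, so they cannot be counted.

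**Can the effect be sized?** Only under assumptions. Let q be the chance that an existing event surfaces at one live contact, the same in every arm, with all contacts attended. With k contacts the captured share is 1 − (1 − q)^k. At equal true risk, the ratio of recorded risks (MBAT arms over the others) is the ratio of these shares. The documents do not give q; I took 0.05 to 0.30.

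| Contacts counted | Others | MBAT arms | q = 0.05 | q = 0.10 | q = 0.30 |
|---|---|---|---|---|---|
| Weeks 1–8, sessions and week 8 visit | 1 | 9 | 7.40 | 6.13 | 3.20 |
| plus 2 nicotine-replacement calls | 3 | 11 | 3.02 | 2.53 | 1.49 |
| plus 3 surveys by phone | 6 | 14 | 1.93 | 1.65 | 1.13 |
| Weeks 1–24, all of these plus visits at weeks 12 and 24 | 8 | 16 | 1.66 | 1.43 | 1.06 |

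Example, third row at q = 0.10: (1 − 0.9^14) / (1 − 0.9^6) = 0.771 / 0.469 = 1.65.

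The model assumes that the event exists before every contact, which overstates the gap. Suppose instead that onset is spread evenly, so that 1 to 8 sessions remain. At q = 0.10 the sessions alone then capture on average 1 − (0.9 + 0.9² + … + 0.9^8)/8 = 1 − 5.126/8 = 0.359. Adding the week 8 visit gives 1 − 0.9 × 0.641 = 0.423, against 0.10 in the other arms. The ratio is 4.2, where the first row has 6.13.

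The direction is the same in every row. The size runs from about 1.1 to about 7, depending on quantities the documents do not state.

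**The case against.** The strongest reply is that the plan reaches every participant more often than the session count suggests. Calls about the mailed nicotine replacement, check-ins, phone surveys and visits at weeks 8, 12 and 24 apply to all arms. Table 6.1 also marks the self-help materials at week 1 for all conditions. This stands, and it narrows the gap considerably. It does not close it, because none of these contacts is described as asking about adverse events and the MBAT arms still have eight more live contacts.

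A second reply is that symptoms are solicited equally in all arms: the withdrawal scale and the affect scale are given at weeks 1, 3, 5, 8, 12 and 24. This stands in part. The scales touch mood, sleep and hunger. But they are described as measures of withdrawal and affect, nothing routes their answers into adverse-event recording, they would not reveal a hospital admission, and Table 6.1 shows no baseline administration of the withdrawal scale.

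A third reply is that the forms sit in an appendix that could not be read, and that a staff log or visit script need not appear in Table 6.1. This stands as a limit. The claim is that no such question is visible, not that none exists.

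Two stronger readings are tempting, and the documents do not support them:
- A reader might count only the orientation and the group sessions, get 9 contacts against 0, and infer that the non-MBAT arms would capture nothing. That count leaves out every all-arm contact, and any capture percentage built on it would also assume that all events begin before the orientation.
- A reader might infer that a planned safety comparison is biased. Section 9 plans none, and the first stopping criterion gives no threshold, test or between-arm rule. The risk is to the interpretation of tabulated events, not to a specified test.

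**Conclusion.** The concern holds in a limited form. Followed as written, the plan gives passive capture of adverse events, with scheduled live contact in weeks 1 to 8 of about 9 in the MBAT arms against 1 in the other two. All-arm contacts reduce the relative imbalance. Recorded rates would tend to be higher in the MBAT arms at equal true risk, and some events in low-contact participants using nicotine products could be missed. The amount cannot be quantified from the documents; the ratios above only show how far it depends on assumption.

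The conclusion rests on two premises: that the appendix forms hold no adverse-event item, and that a live contact gives some chance for an event to surface. It bears on the final safety report and on any judgement under the first stopping criterion. It does not touch the abstinence analyses. This is a change the plan should make, since it costs little and the unequal opportunity is built into the design.

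**What to change.** Add one standard adverse-event and hospitalisation question to the existing REDCap surveys at weeks 1, 3, 5, 8, 12 and 24, worded identically in all four arms. Add a short symptom item at baseline, because the definition turns on what was present then. State in Section 7 who follows up a positive answer, and add the row to Table 6.1. In Section 9, say that adverse events will be summarised by arm from the solicited responses and that spontaneous reports will be listed separately.

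Every arm would then have the same seven scheduled enquiries (baseline plus six), where none is now visible. The cost is a short survey item and staff time to follow up positive answers; no new visit is needed. If the appendix forms already contain such a question, it is enough to cite it in Section 7 and Table 6.1 and to add the sentence on how events will be summarised.
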